Scheduled post-operative assessments following the initial assessment will include a 3 month, 6 month, and one year follow up appointment. Evaluation at the 3-month and 6-month follow-up appointment, will include photos of the surgical site, evaluation of the skin graft and any areas of necrosis or tendon exposure, survey of presence of pain and paresthesia, and the QuickDASH survey. During the 1 year follow-up, in addition the assessments described above, the Vancouver Scale Assessment will be performed by a Co-Investigator who is blinded. Areas of tendon exposure will be treated with xeroform dressing changes.

During surgery and at the scheduled follow up all subjects will have standardized photographs taken utilizing a custom backdrop and a centimeter scale. These pictures will be used to assess wound size and dimension at each encounter, including the original surgery. This will allow us to measure the rate of wound healing, contracture, and rate of skin graft necrosis. The pictures will be analyzed with the SigmaScan planimetry program. This protocol has been previously validated and published.[15]

Subjects will be evaluated by the occupational therapy team prior to their surgery in the pre-operative holding area and during their admission to the hospital. They will be assessed using standard measurement from a goniometer and dynamometer and also given instructions for wrist range of motion exercises. During follow up, subjects will be referred to occupational and physical therapy at the discretion of the attending physician.

Subjects removed from study for unacceptable adverse events will be followed until resolution or stabilization of the adverse event.

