13.0 Statistical Considerations

Endpoints:

1. Rate of tendon exposure. Previously reported from 12-55%. [7, 16-19]
2. Rate and percent of skin graft necrosis. Rate previously reported to be from 7%-51%. [7, 9, 16, 20-22]
Percentage of skin graft loss ranges from $\leq 5\%$ - $\geq 20\%$. [9, 16]
3. Rate of paresthesia. Previously reported to be 36%- 50%. [9, 20]
4. Aesthetic outcome of donor site on Vancouver Scar Scale, a validated objective assessment of scar appearance. [23] Previous scores are reported to be 4.7/13 without Integra and 4.2/13 with Integra. [14, 24]
In particular, we will be focusing on the pliability aspect of the Vancouver Scar Scale, which will be a measure of the functionality of the skin overlying the donor site. The scores will be taken at the 3,6, and 12 month follow up.
5. The Disabilities of the Arm, Shoulder and Hand (DASH) outcome measure is a 30 question survey used to quantify the symptoms and function of any person with musculoskeletal disorders of the upper limb. It is used to determine the impact that a particular disorder has on an individual's life. [25, 26] The QuickDASH is a shortened version of the DASH that has been validated to be as significant as the full questionnaire. [27] While the QuickDash scores of RFFF subjects have not been reported, previous DASH scores have been reported to be 6.93 ± 5.54 in RFFF subjects compared to 2.95 ± 4.42 in non-RFFF subjects. [28]
6. Differences in range of motion at the hand, previously reported to be 22-27 degrees difference [8]
7. Differences in grip and pinch strength in the donor site hand, previously reported to be about a 7kg difference in pinch strength and a 0.75kg difference in grip strength. [29]
8. Wound contracture and Skin Pliability. Normal results are reported below.

Statistical Analysis:

We plan to enroll 50 subjects in each group. All hypothesis testing will two sided and performed at the 0.05 significance level. All analysis will be performed in SAS Version 9.4 (Cary, NC). No interim monitoring is planned for this study.

The analysis and estimated power for each endpoint is described below.

1. Rate of tendon exposure
 - a. We expect about a 25% rate of tendon exposure in the group that does not use Integra, while in the Integra group we hope to have a rate of tendon exposure of below 5%. We will test this hypothesis using a chi-squared test of equal proportions. We will have 81% power to detect this difference with 50 subjects in each group.

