 - a. Range of motion will be measured by resident physicians taking part in the project who will be trained by the occupational therapy team at our institution. The measurements will be taken using electric goniometers so as to standardize the measurements as much as possible.
 - i. Previously reported differences in pre and postoperative range of motion of wrist flexion and extension have ranged from non-statistically significant to about 27 degrees and 22 degrees, respectively.¹
 1. We will expect the difference in wrist flexion and extension in the non-Integra group to be 25 degrees and 20 degrees, respectively.
 2. We will expect the difference in flexion and extension in the Integra group to be 15 and 10 degrees, respectively.[8]
 3. We will again employ two sample t-tests (or Wilcoxon Rank Sum Tests) to test for differences in these angle measurements. Assuming a common standard deviation of five degrees, we will have 99% power to detect a difference in five degrees using a two sample t test.
 - b. Hand strength will be measured by pinch and grip strength dynamometers obtained from the occupational therapy department at our institution. These measurements will be taken at 3 month, 6 month, and 1 year follow up clinic visits.
 - i. Grip strength has been reported to be about a 7kg difference between pre-operative and post-operative measurements, while Pinch strength has been shown to differ by approximately 0.75kg. [29]
 - ii. For the non-integra group, we predict a difference in grip strength of approximately 5kg, while the pinch strength will differ but about 0.75kg
 - iii. For the Integra group, we predict that the difference in grip strength will be approximately 3kg while the pinch strength will differ by approximately 0.25kg.
 - iv. At each time point, we will compare the hand strengths of the Integra and non-Integra groups using two sample t-tests or Wilcoxon Rank Sum Tests as appropriate. Assuming a 5kg grip strength standard deviation in each group, we will have over 99% power to detect differences of 5kg and 7 kg in each group.

The Use of Integra® in Coverage of Radial Forearm Free Flap Donor Site Defect

Comprehensive Cancer Center of Wake Forest University (CCCFWU)

CCCFWU # 99915A

- v. For pinch strength, we assume both groups have a standard deviation of 1kg. To detect a difference 0.75kg, we will have 95% power using a two sample t-test.

7. Wound Contracture and Skin Pliability

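### Wrist motion (item 6a) is compared without adjusting for the pre-operative angle: a valid test, but usually less precise than the planned data allow

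*Combined protocol and SAP*

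**What the plan says.** Item 6a of Section 13.0 introduces wrist motion through "Previously reported differences in pre and postoperative range of motion of wrist flexion and extension". It then gives the size of that difference expected in each arm. For skin graft alone: "We will expect the difference in wrist flexion and extension in the non-Integra group to be 25 degrees and 20 degrees, respectively". For Integra plus graft it gives 15 and 10 degrees. The test is stated as "We will again employ two sample t-tests (or Wilcoxon Rank Sum Tests) to test for differences in these angle measurements". The power statement begins "Assuming a common standard deviation of five degrees" and concludes "we will have 99% power to detect a difference in five degrees using a two sample t test".

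Section 5.0 has the occupational therapy team see subjects before surgery and during the admission: "They will be assessed using standard measurement from a goniometer and dynamometer". A pre-operative measurement is therefore planned, although Section 5.0 does not list the movements recorded. No analysis in Section 13.0 names a baseline covariate.

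**The concern.** Subtracting the pre-operative angle fixes its coefficient at 1. ANCOVA estimates that coefficient from the data. In a randomised comparison with equal arms, ANCOVA is in large samples never less precise than the change score, and it costs one degree of freedom. When the pre/post correlation is below 0.5 and the SDs are equal, the change score is noisier than ignoring the baseline altogether.

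Functional outcome is part of the objective in Section 1.1, so the width of the interval for wrist motion matters, not only whether its test reaches significance. The precision would come from a measurement the trial already intends to take.

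**Working it through.** **Inputs from Section 13.0.** "We plan to enroll 50 subjects in each group"; two-sided 0.05; SD 5 degrees; detectable difference 5 degrees; stated power 99%. The expected between-arm difference is 25 − 15 = 10 degrees for flexion and 20 − 10 = 10 degrees for extension.

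**Not in the documents.** The pre/post correlation ρ, separate pre- and post-operative SDs, and whether the 5 degrees is the SD of a change or of an angle. I assume ρ = 0.3, 0.5 and 0.7, and vary the SD ratio.

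**Step 1: the plan's own figure.** A two-sample t-test with standardised difference 5/5 = 1 and 50 per arm has power 99.86%. The stated 99% reproduces. About 38 per arm would already give 99%. For the expected 10 degrees, power is essentially 100%.

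**Step 2: variance ratio, equal SDs (σ).** Change score: 2(1 − ρ)σ². ANCOVA: (1 − ρ²)σ². Ratio: (1 + ρ)/2.

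| ρ | Ratio | Equivalent n per arm (50 × ratio) | Saving per arm | Interval narrower by (1 − √ratio) |
|---|---|---|---|---|
| 0.3 | 0.65 | 32.5 | 17.5 | 19% |
| 0.5 | 0.75 | 37.5 | 12.5 | 13% |
| 0.7 | 0.85 | 42.5 | 7.5 | 8% |

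Inflating the ANCOVA variance by 1 + 1/96 for estimating the slope lowers the savings to 17.2, 12.1 and 7.1. A simulation (50 per arm, 4,000 runs) gave ratios of 0.656, 0.742 and 0.857.

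**Step 3: unequal SDs.** With the post-operative SD equal to k times the pre-operative SD, the ratio is k²(1 − ρ²)/(1 + k² − 2ρk).

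- k = 1.5: 2.0475/2.35 = 0.871; 1.6875/1.75 = 0.964; 1.1475/1.15 = 0.998. Savings are about 6, 2 and 0 at ρ = 0.3, 0.5 and 0.7.
- k = 0.75: 0.5119/1.1125 = 0.460; 0.4219/0.8125 = 0.519; 0.2869/0.5125 = 0.560. Savings are about 27, 24 and 22.

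The gain vanishes where ρk = 1, because the true slope is then 1 and subtraction is already optimal.

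**Step 4: if post-operative angles alone were compared.** ANCOVA against the unadjusted comparison has ratio 1 − ρ², so the saving is 50ρ² = 4.5, 12.5 and 24.5.

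**Step 5: effect on power, equal SDs.**

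| SD of change | Difference | Change score | ANCOVA, ρ = 0.3 / 0.5 / 0.7 |
|---|---|---|---|
| 5 (plan, read as SD of change) | 5 | 99.86% | 99.999 / 99.99 / 99.97% |
| 10 (assumption) | 5 | 69.7% | 86.7 / 81.6 / 76.6% |
| 15 (assumption) | 5 | 37.9% | 53.5 / 47.8 / 43.3% |
| 15 (assumption) | 10 | 91.0% | 98.4 / 96.8 / 94.7% |

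If the 5 degrees is instead the SD of a single angle, change-score power for 5 degrees at ρ = 0.3 is 98.7% against 99.9% for ANCOVA. At ρ = 0.5 and 0.7 both exceed 99%.

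**The case against.** The strongest reply is that nothing here is broken. In a randomised trial the unadjusted change-score t-test is unbiased with correct type I error, and chance baseline imbalance is already reflected in its standard error. On the plan's inputs power is 99.9% for 5 degrees and about 100% for the 10 degrees expected. Low power appears only if the SD is assumed to be two or three times the planned value. Even at 15 degrees, power for the expected 10 degrees is 91% unadjusted. All of this stands. A reader might infer that the wrist comparison is underpowered or invalid; the documents support neither.

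A reader might also take 7 to 18 subjects as a property of this plan. It is not. It needs both the assumed correlation range and equal SDs, and equal SDs cannot be presumed when one measurement follows surgery.

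Item 6a never formally defines the analysed variable as a change. That also stands, but Step 4 shows that adjustment helps under the other reading too.

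Finally, it is tempting to argue that the correlation must be low because occupational therapy takes the baseline and residents take the follow-up. The documents do not establish this. Section 5.0 has occupational therapy assess before surgery. Item 6a has residents, trained by that team, measure range of motion with electric goniometers, without limiting them to follow-up. Who records the endpoint baseline is unclear, so a change of rater or device is only a possibility.

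**Conclusion.** The point holds as an efficiency recommendation. Item 6a leaves the pre-operative angle out of the model, and adjusting for it would generally tighten the estimate. With equal SDs and ρ of 0.3 to 0.7, both assumed, the gain is worth about 7 to 18 of 50 subjects per arm, or intervals 8% to 19% narrower. Other SD ratios move the saving between about 0 and 27.

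The stated power is not in doubt on the plan's own SD. The practical value is a narrower interval, and insurance if the 5-degree SD, for which item 6a gives no source, is too small. The figures concern the t-test and were not worked for the Wilcoxon alternative.

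**What to change.** Replace the test in item 6a.i.3 with:

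> At each post-operative visit at which range of motion is measured, wrist flexion and extension will each be compared between randomised arms by ANCOVA with the pre-operative angle of the same movement as covariate, reporting the adjusted difference and 95% CI; if residuals are clearly non-normal, a rank-based ANCOVA will be used.

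Keep the change-score t-test or Wilcoxon test as a sensitivity analysis.

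The cost is wording and one degree of freedom, with no new assessment beyond the pre-operative one already planned. Two details should be settled in the same edit, and any analysis of this endpoint needs them. First, name the visits: item 6b gives times for hand strength only, and the 3-month, 6-month and 1-year assessments listed in Section 5.0 do not mention wrist motion. Second, state that the pre-operative assessment records both wrist flexion and extension, who records it and with which device.

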2.3 Inclusion of Women and Minorities

Men and women of all races and ethnicities who meet the above-described eligibility criteria are eligible to participate in this study.

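### The hand-strength comparison in Section 13.0, item 6b.iv makes no stated use of the planned pre-operative reading, which costs precision but does not bias the result

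*Combined protocol and SAP*

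**What the plan says.** Section 13.0, item 6b describes hand strength in terms of change from before surgery. The literature figure is given that way: "Grip strength has been reported to be about a 7kg difference between pre-operative and post-operative measurements", with about 0.75 kg for pinch. The predictions for this trial follow on the same scale: 5 kg (grip) and 0.75 kg (pinch) in the STSG arm, and 3 kg and 0.25 kg in the Integra arm.

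The analysis is stated once, in item 6b.iv: "At each time point, we will compare the hand strengths of the Integra and non-Integra groups using two sample t-tests", with the Wilcoxon test as the alternative. The item names no change score, no baseline covariate and no comparison with the other hand. The visits listed in item 6b are all post-operative: "These measurements will be taken at 3 month, 6 month, and 1 year follow up clinic visits".

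A baseline does appear in Section 5.0: "Subjects will be evaluated by the occupational therapy team prior to their surgery in the pre-operative holding area", with a goniometer and a dynamometer. That section does not say whether pinch is measured as well as grip, or which hand is tested.

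The SDs used for power are 5 kg (grip) and 1 kg (pinch). The plan does not say whether they describe strength at a visit or change from baseline.

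**The concern.** Taken at its word, item 6b.iv tests strength at 3, 6 and 12 months and leaves the pre-operative reading out of the analysis. Eligibility is broad: adults of any age from 18, needing the flap for cancer, trauma, chronic wounds or other reasons, and "Men and women of all races and ethnicities who meet the above-described eligibility criteria are eligible". Patients may therefore differ in strength for reasons unrelated to the donor site, and a baseline reading is the usual way to remove part of that variation.

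Two things are at stake. The first is precision on a functional outcome, which belongs to the primary objective in Section 1.1. The second is clarity. Two analysts following the text could test different variables, one post-operative strength and the other loss from baseline, and nothing in the plan settles the choice before the data are seen.

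**Working it through.** **Inputs from Section 13.0.** Group size: "We plan to enroll 50 subjects in each group". Test level: "All hypothesis testing will two sided and performed at the 0.05 significance level". Grip SD 5 kg, pinch SD 1 kg. Predicted losses as above. No dropout allowance is stated, so all figures assume 50 evaluable patients per arm.

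**Assumed input.** The pre/post correlation r is not in the documents. I show 0.5 to 0.8, with equal SDs before and after surgery.

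**Method.** Power of the two-sample t-test from the noncentral t distribution with 98 degrees of freedom and noncentrality d / (SD × √(2/50)) = 5d / SD.

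**Step 1: the plan's own figures.**
- Grip, d = 5 kg: noncentrality 5 × 5/5 = 5.0, power 99.9%. For 7 kg it is above 99.99%. The plan says over 99%.
- Pinch, d = 0.75 kg: noncentrality 5 × 0.75/1 = 3.75, power 96.0%. The plan says 95%.

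The figures reproduce, but for differences of the size of a pre/post loss, not a difference between arms. That is a separate matter and is not counted here.

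**Step 2: the between-arm effect the plan predicts.** Grip 5 − 3 = 2 kg. Pinch 0.75 − 0.25 = 0.5 kg. Under randomisation the arms have the same expected baseline, so the expected difference in post-operative strength equals the expected difference in loss. An unadjusted, a change-score and a baseline-adjusted comparison all target the same 2 kg and 0.5 kg.

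**Step 3: stated SDs read as SDs of raw strength.**
- Unadjusted: grip noncentrality 5 × 2/5 = 2.0, power 51%; pinch 5 × 0.5/1 = 2.5, power 70%.
- ANCOVA: residual SD = SD × √(1 − r²).
- Change score: SD × √(2(1 − r)).

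| r | Grip ANCOVA SD (kg) | Grip ANCOVA | Grip change | Pinch ANCOVA | Pinch change |
|---|---|---|---|---|---|
| 0.5 | 4.33 | 63% | 51% | 82% | 70% |
| 0.7 | 3.57 | 79% | 73% | 93% | 89% |
| 0.8 | 3.00 | 91% | 88% | 98% | 97% |

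In interval terms, the 95% CI half-width for grip is 1.984 × 5 × √(2/50) = 1.98 kg unadjusted, about the size of the predicted effect. At r = 0.8 it is 1.984 × 3 × √(2/50) = 1.19 kg.

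**Step 4: 5 kg read as the SD of change.** The implied raw SD is 5 / √(2(1 − r)). A change score then has 51% power for 2 kg whatever r is.

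| r | Implied raw SD (kg) | Raw comparison | Change score | ANCOVA |
|---|---|---|---|---|
| 0.5 | 5.0 | 51% | 51% | 63% |
| 0.7 | 6.5 | 34% | 51% | 57% |
| 0.8 | 7.9 | 24% | 51% | 55% |

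Under both readings ANCOVA is at least as precise as either alternative, apart from the loss of one degree of freedom. A change score beats the raw comparison only when r exceeds 0.5.

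**The case against.** The best defence is that the plan never says raw strength is to be tested. Item 6b.iv follows three lines about pre/post differences, its power sentence uses values of that kind, and endpoint 7 at the start of Section 13.0 is worded as differences in strength. A t-test on change at each visit is a plausible intention. This stands in part: the unadjusted comparison is the literal reading, not an established intention. But if change was meant, the item still does not say so, and ANCOVA would still be the more precise choice, though with the smaller gain of Step 4 (51% to 55–63%).

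Three stronger inferences are tempting and are not supported.

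- A reader might infer that differences between people overwhelm the treatment effect. At the plan's own SDs the effects are 0.4 SD (2/5) and 0.5 SD (0.5/1). A much worse picture needs a larger raw SD or a particular correlation, and the documents give neither. Nor can one say that baseline removes most of the variance: the share removed is r², which is 25% at r = 0.5, 49% at 0.7 and 64% at 0.8.
- A reader might infer that the wrong quantity is tested, or that chance imbalance in sex or age biases the result. Step 2 answers the first. As to the second, the unadjusted comparison is unbiased under randomisation, and its interval already allows for chance imbalance. The price is a wider interval.
- A reader might blame the missing baseline for the fall from over 99% to 51% for grip. That fall comes from putting 2 kg in place of 5 or 7 kg at the same SD.

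It is also fair to say that the baseline is not fully secured by the text, since Section 5.0 names neither pinch nor the hand tested.

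**Conclusion.** The point holds as a gap in specification and a loss of precision. Item 6b.iv does not define the variable analysed and states no use of the pre-operative reading that Section 5.0 plans. Read literally, it is valid but less precise than it need be.

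The size depends on what the stated SDs mean. If they are raw SDs, baseline adjustment raises power from 51% to 63–91% for grip and from 70% to 82–98% for pinch. If 5 kg is the SD of change, ANCOVA gives 63–55% for grip as r goes from 0.5 to 0.8. The gain is then modest over a change score (51%) and larger over a raw comparison (51–24%). These ranges rest on assumed correlations of 0.5–0.8, equal SDs before and after surgery, and 50 evaluable patients per arm. That ANCOVA does not lose precision holds for any correlation, apart from one degree of freedom.

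**What to change.** In item 6b.iv, state that donor-hand grip and pinch at each visit are compared by ANCOVA with the same hand's pre-operative value as covariate (rank-based ANCOVA if the data are clearly non-normal), and that the adjusted between-arm difference is reported with its 95% CI. State whether the 5 kg and 1 kg SDs refer to strength or to change.

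In Section 5.0 and item 6b, confirm that pre-operative grip and pinch of the donor hand are both recorded, by the same method as at follow-up, and add the pre-operative reading to the visits listed in 6b.

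Apply the same rule to wrist flexion and extension in item 6a.i.3. First reconcile the measurement: Section 5.0 has the occupational therapy team assess patients before surgery with a goniometer, while item 6a has trained residents use electric goniometers.

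The cost is a few sentences. If pre-operative grip and pinch of the donor hand are already part of the planned assessment, no new measurement is needed; if not, it is a short addition to a visit that already takes place.

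### Grip and pinch power (over 99% and 95%) is computed on pre-to-post changes, not on the predicted difference between arms, where it is about 51% and 70%

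*Combined protocol and SAP*

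**What the plan says.** Section 13.0 sets the common terms: "We plan to enroll 50 subjects in each group" and "All hypothesis testing will two sided and performed at the 0.05 significance level".

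Item 6b covers hand strength. Item 6b.i cites published pre- to post-operative changes of about 7 kg for grip and 0.75 kg for pinch. Items 6b.ii and 6b.iii then give the plan's own predictions by arm:

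- Non-Integra: "we predict a difference in grip strength of approximately 5kg, while the pinch strength will differ but about 0.75kg".
- Integra: "we predict that the difference in grip strength will be approximately 3kg while the pinch strength will differ by approximately 0.25kg".

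The test is between arms: "At each time point, we will compare the hand strengths of the Integra and non-Integra groups using two sample t-tests", or Wilcoxon rank sum tests where appropriate.

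The power statements are as follows:

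- Grip, SD 5 kg in each group: "we will have over 99% power to detect differences of 5kg and 7 kg in each group".
- Pinch, SD 1 kg in both groups: "To detect a difference 0.75kg, we will have 95% power using a two sample t-test".

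Section 5.0 (Study Outcomes and Study Measures) places an occupational therapy assessment before surgery and during the admission: "They will be assessed using standard measurement from a goniometer and dynamometer". The hand-strength analysis in item 6b does not mention adjusting for that pre-operative value.

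**The concern.** A two-sample t-test has power against the difference between the two arm means. The plan's predictions put that difference at 2 kg for grip and 0.5 kg for pinch, and item 6b gives power for neither. It gives power for larger numbers that describe how far a hand changes from before to after surgery, which this test does not estimate.

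Functional outcome is half of the primary objective in Section 1.1, and no single primary endpoint is named. With power stated as over 99% and 95%, a non-significant grip or pinch result would be read as strong evidence that Integra gives no benefit. If the predicted effects are real, the test at a given visit would miss the grip benefit about half the time and the pinch benefit about 30% of the time.

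**Working it through.** **Inputs, all from Section 13.0.** n = 50 per arm; two-sided alpha 0.05; SD 5 kg (grip) and 1 kg (pinch); predicted pre-to-post changes 5 vs 3 kg (grip) and 0.75 vs 0.25 kg (pinch).

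**Formula.** For a two-sample t-test with n per arm, the noncentrality is d / (SD × √(2/n)) on 2n − 2 = 98 degrees of freedom. With n = 50, √(2/50) = 0.2, so the noncentrality is d / (0.2 × SD). The critical value is 1.984. Power is the probability that a noncentral t variable exceeds it in absolute value.

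**Step 1: reproduce the plan's figures.**

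| Outcome | d entered | SD | Noncentrality | Power | Plan states |
|---|---|---|---|---|---|
| Grip | 5 kg | 5 kg | 5 / 1 = 5.00 | 99.9% | over 99% |
| Grip | 7 kg | 5 kg | 7 / 1 = 7.00 | above 99.9% | over 99% |
| Pinch | 0.75 kg | 1 kg | 0.75 / 0.2 = 3.75 | 96.0% | 95% |

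The figures reproduce as between-arm t-tests with 50 per arm. The formula is right; the question is the d that went into it.

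**Step 2: trace each d.** The 5 kg equals the non-Integra arm's predicted change. The 7 kg equals the published pre-to-post change and is predicted for neither arm. The 0.75 kg is both the published change and the non-Integra prediction. None is a difference between arms.

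**Step 3: the contrast the test addresses.** Grip: 5 − 3 = 2 kg. Pinch: 0.75 − 0.25 = 0.5 kg. Because randomisation makes the pre-operative means equal in expectation, these are the expected between-arm differences whether follow-up values or changes are compared.

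| Outcome | d | SD | Noncentrality | Power |
|---|---|---|---|---|
| Grip | 2 kg | 5 kg | 2 / 1 = 2.00 | 50.8% |
| Pinch | 0.5 kg | 1 kg | 0.5 / 0.2 = 2.50 | 69.7% |

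**Step 4: what 50 per arm can detect.** At 80% power the detectable differences are 2.8 kg (grip) and 0.57 kg (pinch), both above the predicted effects. Reaching 80% at the predicted effects would take about 100 per arm for grip and 64 for pinch. The plan gives no dropout allowance; assuming 40 to 45 evaluable per arm, power falls to about 42–47% (grip) and 60–65% (pinch).

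**Step 5: sensitivity to what the SD means.** The plan does not say whether 5 kg and 1 kg are SDs of strength or of change. Suppose they are SDs of strength, equal before and after surgery, with pre/post correlation ρ. The SD of change is then SD × √(2(1 − ρ)), and the residual SD under ANCOVA is SD × √(1 − ρ²). The documents give no ρ, so these values are assumptions:

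| ρ (assumed) | Grip, change | Grip, ANCOVA | Pinch, change | Pinch, ANCOVA |
|---|---|---|---|---|
| 0.3 | 39% | 55% | 55% | 74% |
| 0.5 | 51% | 63% | 70% | 82% |
| 0.7 | 72% | 79% | 89% | 93% |
| 0.8 | 88% | 91% | 97% | 98% |

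Grip power above 99% on change scores would need ρ of about 0.9.

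**The case against.** The best defence has five parts.

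- **The arithmetic is correct for the inputs used.** This is true, as Step 1 shows. The fault lies in the effect size entered. The plan does not say where its inputs came from, so their origin is inferred from matching numbers. The inference is not essential, because no power is given for the predicted between-arm differences and no reason is given for larger targets.
- **The SDs are ambiguous, so 51% and 70% are not certain.** The ambiguity is real, and Step 5 gives the range. But the plan tests hand strength at each time point and applies 5 kg and 1 kg as the SD of that quantity; 51% and 70% follow from its own method.
- **There are three visits.** The miss rates are per visit. If the effect held at 3, 6 and 12 months, with an assumed between-visit correlation of 0.5 to 0.9, the chance of at least one significant grip result would be about 61–76%. That is gained only by leaving multiplicity uncorrected, and it is still far from 99%.
- **An unadjusted t-test is valid in a randomised trial, and ANCOVA is a separate request.** The power error does stand without ANCOVA. The range-of-motion statement is conservative, powering 5 degrees against a predicted 10, so ANCOVA there is for consistency and precision. Section 5.0 does not name pre-operative pinch, although the predicted pre-to-post pinch change presupposes it.
- **The plan accepts low power elsewhere** (62%, 16%, 29% and 39%), so honest figures need not alter the design. Agreed. That candour is the reason to correct item 6b: it overstates power where those items disclose that it is low.

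**Conclusion.** The concern holds. Item 6b states power for effects larger than those it predicts. At its own predicted between-arm differences, power per visit is about 51% for grip (stated as over 99%) and about 70% for pinch (stated as 95%). These figures assume 50 evaluable subjects per arm, normal data, and that the stated SDs are those of the quantity compared, as the plan's calculation takes them. Other readings of the SD move the figures, but none restores grip power above 99% without a pre/post correlation near 0.9 that the plan does not state. The power statements are wrong as written and must be corrected.

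**What to change.** 1. In items 6b.iv and 6b.v, restate power for the predicted between-arm differences: about 51% for 2 kg grip (SD 5 kg) and about 70% for 0.5 kg pinch (SD 1 kg). If a larger between-arm difference is the intended target, state it and justify it.
2. Say whether each SD refers to the strength value or to the change from the pre-operative value.
3. Replace the unadjusted t-tests for grip, pinch and range of motion with ANCOVA of the follow-up value on arm, adjusted for the pre-operative value. If the SDs are those of post-operative values and the baseline correlation is 0.5 to 0.8 (an assumption), power rises to about 63–91% for grip and 82–98% for pinch.
4. Name pinch explicitly in the pre-operative assessment in Section 5.0, so that the baseline for item 3 is certain to exist.

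The cost is SAP wording and a less favourable stated power. Enrolment need not change. ANCOVA needs no new data, provided the pre-operative dynamometer assessment includes pinch.
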